Date: 04.05.2020 Version: 3

STATISTICAL ANALYSIS PLAN

Study name: Evaluation Of The Effectiveness And Safety Of Adding Ivermectin to

Treatment in Severe COVID-19 Patients

Study protocol cod: IVMC_03

Ethics committee approval number and date: 139/03.04.2020

Coordinator researcher: [name]. [name]

STATISTICAL ANALYSIS PLAN

Convenience Sampling method will be used in the study. Unilateral blinding will be made in determining which of the study and control groups participating patients will be included in the study, those with an odd number will be included in the study group, and those with an even number will be included in the control group.

In determining the sample size, it was planned to include 30 individuals in each group based on the number of available kits. In this case, the values of 0.05 for Type I Error Rate, 0.67 for Effect Size and 0.80 for Power were reached.

The Chi-Square test will be used in the evaluation of categorical data, the Wilcoxon test for in-group comparisons, and the Mann-Whitney U test for intergroup comparisons. For statistical significance, the value of p=0.05 will be taken into account and the analyzes will be carried out in the SPSS 20.0 package program.

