In a recently published in vitro study from Australia, the efficacy of ivermectin used as an antiparasitic agent on SARS-CoV-2 was evaluated and Vero/hSLAM cells were infected with this virus in vitro and exposed to ivermectin, after 48 hours there was a 99.8% reduction in viral load. Based on these studies, it can be thought that ivermectin, which has also been shown to have antiviral efficacy in different studies, may also be effective in COVID19 patients (8).

In this study, it is aimed to evaluate the effect of ivermectin addition to the "Hydroxychloroquine ± Favipiravir ± Azithromycin" combination therapy, which is the reference treatment recommended in the "Covid19 Guideline" prepared by the Ministry of Health, on clinical response in patients with severe COVID19 pneumonia and to investigate the safety of ivermectin use in these patients (10).

Material and Method

The study will be conducted as a prospective, randomized, controlled, single-blind Phase 3 study. Patients with severe COVID19 disease who were hospitalized in Afyonkarahisar Health Sciences University, Health Sciences University Istanbul Sultan Abdülhamid Han Training and Research Hospital, Ankara City Hospital and Health Sciences University Ankara Gülhane Training and Research Hospital COVID19 service and intensive care units will be included in the study.

There will be two patient groups in the study, the study arm and the control arm. A total of 60 patients, including 30 in both arms, are planned to be included in the study.

Patient Selection and Inclusion Criteria

Patients who were hospitalized with a pre-diagnosis of *severe COVID-19 pneumonia and thereafter diagnosis of COVID-19 was also confirmed microbiologically with PCR positivity in respiratory tract samples were included into the study (13). They were randomized to the study and control group, respectively.

- * Patients with at least one of the criteria below were accepted as patients with severe COVID-19 pneumonia;
- a. Presence of tachypnea ≥30/minute, SpO2 level <90% in room air, PaO2/FiO2 <300 in oxygen receiving patient
- b. Presence of specific radiological finding for Covid-19 in lung tomography (bilateral lobular, peripherally located, diffuse patchy ground glass opacities)
- c. Mechanical ventilation requirement
- d. Acute organ dysfunction findings; patients with SOFA (sepsis-related organ failure assessment) score> 2

THE SEQUENTIAL ORGAN FAILURE ASSESSMENT (SOFA) SCORE

0	1	2	3	4

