> 400	<400	<300	<200 (26.7)	<100 (13.3)
(53.3)	(53.3)	(40)	with respiratory support	with respirator support
≥150	<150	<100	<50	<20
<1.2	1.2-1.9	2.0-5.9	6.0-11.9	>12.0
(20)	(20-32)	(33-101)	(102-204)	(204)
MAP	MAP	Dopamine <5	Dopamine 5.1 - 15 or	Dopamine >15
≥70mmHg	<70mmHg	or Dobutamine	Epinephrine ≤ 0.1 or	or Epinephrine
		(any dose)	Norepinephrine ≤ 0.1	>0.1 or Norep nephrine >0.1
15	13-14	10-12	6-9	<6
<1.2 (110)	1.2 -1.9	2.0 - 3.4 (171-	3.5 - 4.9	> 5.0 (440)
	(110-170)	299)	(300 -440)	<200
	(110 110)		<500	1200
	≥400 (53.3) ≥150 <1.2 (20) MAP ≥70mmHg	≥400 <400 (53.3) (53.3) ≥150 <150 <1.2 1.2-1.9 (20) (20-32) MAP MAP ≥70mmHg <70mmHg	≥400	≥400

Mutations in the mdr1 / abcab1 gene and the CYP3A4 gene will be investigated in patients who meet any of the above criteria and are > 18 years of age and enrolled in the study group by randomization. Patients with mutations will not be included in the study.

Exclusion Criteria

Patients with the following characteristics were excluded from the study.

- 1. Pediatric patients; <18 years of old
- 2. Patients with chronic liver or kidney disease
- 3.Pregnant women
- 4. Patients with known ivermectin allergy

Genetic study

In the patients included in the study group, the mutation in 29 pairs of primers and the haplotypes and mutations of the CYP3A4 gene will be investigated by performing sequence analysis in the mdr1 / abcab1 gene with the Sanger method.

Design of Primers

"PRIMER © – Primer Designer v.2.0 (Scientific & Educational Software)" software will be used in primer design for mutation research. Primers will be synthesized by Metabion International AG. Sequence analysis plan and primer design will be made, including the coding regions of these genes, exon-intron junction regions.

Sanger Sequence Analysis

DNA fragments for all patients will be sequenced with the ABI 3130 sequence analyzer after amplification using polymerase chain reaction (PCR) followed by bidirectional fluorescent markers using BigDye chemistry (Life Technologies, Carlsbad, CA, USA). The sequences will be read with the Seqscape program. Variants obtained here will be analyzed according to ACMG criteria and variants will be classified. In the analysis of variants, data will also be evaluated using relevant databases to identify known haplotypes.

Treatment and patient follow-up

The following reference treatment recommended by the Ministry of Health will be applied to all patients in the control and study groups;

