- 1. Hydroxychloroquine (2x400mg loading dose followed by 2x200mg, po, 5 days)
- 2. Favipiravir (2x1600mg loading followed by 2x600mg, po, maintenance dose for a total of 5 days)
- 3.Azithromycin (500mg first day followed by 250mg / day 4 days, po, 5 days total)

In addition to the reference therapy, ivermectin at a dose of 200 mcg / kg / day (9 mg between 36-50 kg, 12 mg between 51-65 kg, 15 mg between 66-79 kg,> 80 kg 200mcg / kg) It will be applied for five days in the form of a solution prepared for enteral use (Ivermectin 5mg/5ml solution was manufactured by Neutec Pharmaceutical-Turkey, under GMP conditions).

Patients in the control arm will be given reference treatment with the other 3 drugs without giving ivermectin.

The drug whose effectiveness will be evaluated in the study is ivermectin. Ivermectin is an FDA-approved antiparasitic drug. Approved adult dose in parasitic infections is reported as 200mcg / kg / day (11). Although ivermectin has been shown to be effective in SARS CoV-2 in vitro, there is no randomized prospective controlled study showing that it is effective in COVID19 patients. In a very recent study that is still in press, it has been reported that it significantly reduces mortality in COVID19 patients, and in this study, no information is given about the duration and dosage of use (12).

In a study conducted in Thailand on the use of ivermectin in dengue fever infection, it was reported that it was used at doses of 200mcg / kg / day and 400mcg / kg / day (13).

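### The trial is called randomized, but its only allocation rule is odd number to ivermectin and even number to control, with no random sequence and no concealment described

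*SAP*

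**What the plan says.** The protocol (Material and Method) states: "The study will be conducted as a prospective, randomized, controlled, single-blind Phase 3 study". Under Patient Selection and Inclusion Criteria it adds: "They were randomized to the study and control group, respectively". The mutation-testing paragraph in the same section refers to patients "enrolled in the study group by randomization. Patients with mutations will not be included in the study". None of these places gives a method: there is no sequence generation, list, blocking, stratification, central service or envelope system.

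The method appears only in the first paragraph of the SAP. Sampling is described as "Convenience Sampling method will be used in the study". Allocation is by parity: "those with an odd number will be included in the study group, and those with an even number" going to control. The same sentence says "Unilateral blinding will be made in determining which of the study and control groups participating patients will be included in the study", without saying who is blinded or by what means.

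Recruitment is at four hospitals, from "COVID19 service and intensive care units will be included in the study". On treatment, the protocol says: "Patients in the control arm will be given reference treatment with the other 3 drugs without giving ivermectin". No placebo is mentioned.

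**The concern.** An odd/even rule is not a random sequence unless the number itself is random, and the SAP does not say that it is. It does not say whether the number is an enrolment, admission or file number, who issues it across four hospitals, or whether the recruiter sees it before deciding to enrol. If it is sequential or visible beforehand, the recruiter knows the arm before approaching the patient.

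That matters here because prognosis will vary widely. A patient can qualify as severe on a tomography finding alone or because of mechanical ventilation. A recruiter who can foresee the arm can steer milder or sicker patients to one side, knowingly or not. The SAP names only chi-square, Wilcoxon and Mann-Whitney tests, none adjusted for baseline severity. The plan therefore has no means of separating a drug effect from selection on prognosis.

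**Working it through.** **The plan's own figures.** None of them bears on allocation. The sample size (30 per arm, effect size 0.67, power 0.80) is unaffected by how patients are allocated, so replacing the rule changes neither N nor power.

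**Step 1: set the passages side by side.** The protocol uses the word randomized, or a form of it, in three places and gives a mechanism in none. The SAP gives a mechanism, parity of a number, which is random only if the number is. The claim of blinding at allocation comes with no procedure. After allocation, one arm receives an enteral ivermectin solution and the other receives nothing in its place, and the blinded party is not named.

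**Step 2: how predictable is the rule?** Assume the number is the enrolment order. Odd/even is then one fixed alternating sequence, and 60 of 60 assignments (100%) can be foreseen. For comparison, take a recruiter who knows the block size and all past assignments. The expected share of correct guesses is about 71% with unconcealed blocks of 4, about 68% with unconcealed blocks of 6, and 50% with simple randomization or a fully concealed list.

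**Step 3: what could an imbalance do?** The documents give no figure for this, so the inputs are assumptions: no drug effect, 30 per arm, response 0.70 in good-prognosis and 0.30 in poor-prognosis patients. If an arm has an expected good-prognosis share g, its response rate is

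p = 0.70g + 0.30(1 − g).

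For shares of 60% and 40%: 0.70 × 0.60 + 0.30 × 0.40 = 0.54, and 0.70 × 0.40 + 0.30 × 0.60 = 0.46, a spurious difference of 8 points.

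The rejection rate is the exact sum, over all 31 × 31 outcomes of two independent binomials with n = 30, of those where the two-sided chi-square test (1 df) is significant at 0.05. The SAP does not say whether the continuity correction applies, so both versions are shown.

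| Good-prognosis shares | Response rates | Spurious difference | Uncorrected | Corrected |
|---|---|---|---|---|
| 50/50 | 0.50 vs 0.50 | 0 points | 5.2% | 2.7% |
| 55/45 | 0.52 vs 0.48 | 4 points | 6.3% | 3.5% |
| 60/40 | 0.54 vs 0.46 | 8 points | 9.8% | 5.9% |
| 65/35 | 0.56 vs 0.44 | 12 points | 15.7% | 10.1% |
| 70/30 | 0.58 vs 0.42 | 16 points | 24.2% | 16.7% |

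**Step 4: sensitivity.** At 60/40 shares, response of 60% versus 40% by prognosis gives 0.52 vs 0.48 and an uncorrected rate of 6.3%. Response of 80% versus 20% gives 0.56 vs 0.44 and 15.7%.

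The table treats the shares as expected values. If the realised numbers of good-prognosis patients are fixed instead, with response 0.70 and 0.30, the uncorrected rates are 3.4% at 15 vs 15, 7.7% at 18 vs 12 (4.3% corrected) and 22.5% at 21 vs 9.

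**The case against.** The strongest reply is that the documents do not prove non-random allocation. If the number were drawn at random, or issued only after irrevocable enrolment, parity could give a valid assignment. The protocol does say randomized, and the SAP does mention blinding at this step. That is a fair limit on the conclusion: what is shown is that random generation and concealment are undocumented and that the stated rule reads as quasi-random. It does not rescue the plan, because neither document describes such a number and the blinding phrase names no mechanism.

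Other points are partly right:

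- Convenience sampling concerns who enters the trial, not which arm they join, so it is not itself an allocation defect. It does leave the recruiter discretion over entry, which is how a foreseeable arm turns into selection.
- The illustrative error rates rest on chosen inputs. With fixed realised shares, a moderate imbalance need not push the corrected test above 5%. They show direction and possible scale and should not set the severity of the point.
- Baseline demographics, comorbidities, laboratory values and tomography are recorded (protocol, Study Design), and some outcomes are changes from baseline. Measured imbalance would therefore be visible. The planned tests would still not adjust for it, and unmeasured selection would stay hidden.
- Single-blind does not require a placebo, since an outcome assessor could be the blinded party. The valid complaint is that nobody is named.

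**Conclusion.** The concern holds and should be corrected before patients are allocated. As written, the randomized label is unsupported: the one operational rule makes the arm foreseeable on its natural reading, and no concealment is described. Full predictability (60 of 60) depends on the number being the enrolment order, and more generally foreseeability depends on its being sequential or visible before enrolment.

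The size of any resulting bias cannot be derived from the documents. Under the stated assumptions, the uncorrected false-positive rate runs from 6.3% to 24.2% as the expected imbalance grows from 55/45 to 70/30. The conclusion does not depend on these figures.

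**What to change.** Replace the odd/even rule with a computer-generated sequence, for example permuted blocks of varying size. Keep it from recruiters, either with someone outside enrolment or in sequentially numbered opaque sealed envelopes, until consent and all criteria assessed before allocation are recorded. Any properly concealed random sequence would serve.

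The list can be central or one per centre. Separate lists can leave unequal totals: with blocks of 4, for instance, an unfinished block can leave a centre out by 2, so four centres could be out by 4 × 2 = 8, or 34 versus 26. This matters because the SAP set 30 per group by the kits available.

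State who is blinded and how, or drop the single-blind label.

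Reconcile the new procedure with the protocol's mutation testing, which follows allocation and excludes patients from the study arm only. A concealed list does not remove that imbalance.

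If patients have already been allocated by parity, define the number and describe that part of the trial as quasi-randomized. Add a comparison adjusted for one pre-specified baseline severity measure such as SOFA, and state that adjustment cannot remove unmeasured selection.

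The cost is a short amendment to protocol and SAP and a few hours to prepare the list or envelopes, plus the effort of putting concealment in place at four hospitals. No extra patients or visits are needed. Reconciling the mutation testing may cost more: if the sponsor settled mutation status before allocation, roughly 30 control patients would also need sequencing, and allocation would wait for the result.

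### The unstratified chi-square is valid but ignores respiratory support at entry, which may cost power and leaves chance imbalance uncorrected

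*SAP*

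**What the plan says.** The Protocol (Material and Method) recruits from four hospitals; patients in their "COVID19 service and intensive care units will be included in the study". Under Patient Selection and Inclusion Criteria any one of four alternatives is enough for severe disease. A tomography finding alone qualifies, and so does "Mechanical ventilation requirement". The sample size is given as "A total of 60 patients, including 30 in both arms, are planned to be included in the study".

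The SAP allocates by patient number: "those with an odd number will be included in the study group, and those with an even number will be included in the control group". It mentions no stratification by hospital, ward or support. On analysis it says "The Chi-Square test will be used in the evaluation of categorical data", adds Wilcoxon and Mann-Whitney tests, and stops there. It does not link a test to the primary endpoint by name, but day-5 clinical response is binary and falls under the chi-square sentence, as does mortality.

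The number of patients cannot readily be raised: "it was planned to include 30 individuals in each group based on the number of available kits".

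**The concern.** Day-5 response probably depends heavily on the support a patient needs at entry. The Protocol (Study Design, primary endpoint) requires at least two of several criteria. A patient who qualified on tomography alone may already meet the respiratory-rate and room-air saturation criteria at entry. A ventilated patient cannot show a room-air saturation until off support. This is inference, since the documents give no rates, but it makes a sizeable contrast plausible.

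A test that ignores such a factor can lose power that a trial of 60 cannot spare. When the arms happen to differ in entry support, it also attributes that difference to the drug.

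**Working it through.** **The plan's own figure.** The SAP reports that "the values of 0.05 for Type I Error Rate, 0.67 for Effect Size and 0.80 for Power were reached". It names neither the effect-size metric nor the sidedness. Read as a standardised difference with 30 per arm, 0.67 × √(30/2) = 2.595.
- One-sided: Φ(2.595 − 1.645) = 0.829 (normal); the Mann-Whitney version (n × 3/π, noncentral t) gives 0.805, which matches 0.80.
- Two-sided: Φ(2.595 − 1.960) = 0.737.

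The stated power therefore fits a one-sided, continuous-type comparison. It says nothing about a binary response in mixed strata, so the size of this point has to be simulated.

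**Inputs.** From the documents: 30 per arm, α = 0.05, plain chi-square, no stratification. Assumed, because the documents give none: stratum sizes, control response by stratum, and a common odds ratio of 4. Trials were simulated with a random 30:30 split, 100,000 to 200,000 per setting in the table below.

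**Tests.** Plain Pearson chi-square against 3.84. For Cochran-Mantel-Haenszel (CMH), stratum s has a responders among n1 treated patients, n0 controls, m responders in all and T patients:
- D = a − n1·m/T
- V = n1·n0·m·(T − m) / [T²(T − 1)]
- statistic (ΣD)²/ΣV against 3.84. The continuity-corrected form uses (|ΣD| − 0.5)² instead.

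**Power at odds ratio 4**

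| Patients per stratum (most severe first) | Control response | Plain | CMH | Gain (points) |
|---|---|---|---|---|
| about 24/36 | 30/40% | 0.746 | 0.740 | −0.6 |
| 30/30 | 20/65% | 0.557 | 0.638 | 8 |
| 24/36 | 20/70% | 0.484 | 0.589 | 10.5 |
| 24/36 | 15/75% | 0.380 | 0.524 | 14 |
| 20/40 | 10/75% | 0.305 | 0.470 | 16.5 |
| 6/44/10 | 20/50/70% | 0.637 | 0.657 | 2 |
| 6/34/20 | 15/50/70% | 0.586 | 0.626 | 4 |
| 12/24/24 | 15/40/60% | 0.626 | 0.665 | 4 |
| 10/30/20 | 15/50/75% | 0.531 | 0.604 | 7 |
| 12/24/24 | 10/45/75% | 0.468 | 0.575 | 11 |

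Milder two-stratum contrasts at 24/36 gain about 1 point (30/50%) and 3.5 points (30/60%). In a wider scan, with plain power held near 0.74, the ventilated share at 10–50% and contrasts up to 5% versus 80%, the gain ran from −1 to +21 points. Type I error was close to 0.05 for both tests throughout.

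**Continuity correction.** At 24/36 the corrected CMH has power 0.381 (15/75%) and 0.456 (20/70%). The gain is gone, and type I error falls to about 0.02.

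**Chance imbalance.** With K severe-support patients among 60, the number in one arm is Hypergeometric(60, K, 30), and the difference between arms is 2k − K. P(|difference| ≥ 6) is 0.170, 0.187 and 0.196 for K = 20, 24 and 30, but about 0.08 for K = 10 and 0.02 for K = 6.

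With no drug effect, a six-patient imbalance shifts the expected response difference by 6 × (0.75 − 0.15)/30 = 0.12 at 15/75%, or 6 × (0.70 − 0.20)/30 = 0.10 at 20/70%. Given that imbalance at K = 24, the plain test rejects in 9–11% of trials; at eight patients, in 15–19%. CMH stays near 5% in both cases.

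**Adding hospital.** With ventilation crossed with four hospitals (eight strata, no hospital effect, a constant 30-point benefit), the change against the plain test is about −3 to +8 points, compared with +1 to +13 for ventilation alone.

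**The case against.** An unstratified primary test is legitimate, and the strong contrast is not demonstrated. Response needs any two criteria, so a ventilated patient may respond without extubation. The plain test holds its error rate over all trials, and with no drug effect the two tests reach different conclusions in only 1–7% of trials. All of this stands.

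Two stronger readings are tempting. A reader might infer that the plan loses 10 to 15 points of power. The documents give neither the ventilated share nor response by support, so no fixed loss follows; the table runs from slightly negative to 16.5. A reader might also infer that chance imbalance would decide the primary result. The raised false-positive rates apply only to trials that happen to be imbalanced. The 17–20% frequency needs 20 to 30 severe-support patients, and unconditional type I error stays near 0.05. The accurate statement is that imbalance can distort the result in a minority of trials.

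It is also fair to object that the stratifying variable is not securely planned. The baseline list in the Protocol's Study Design omits respiratory support, and respiratory findings on treatment day 1 are not said to precede the first dose.

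**Conclusion.** The point holds as an efficiency improvement. The planned test is valid, but it sets aside a probable strong predictor in a trial whose size is limited by supply. The expected gain is about zero if support is weakly prognostic, roughly 4 to 11 points in most three-stratum examples (2 in one with few patients at the extremes), and about 8 to 16 points under the strong contrast. These figures rest on assumed rates, an odds ratio of 4 common to all strata, and random 30:30 allocation. Mortality was not simulated separately.

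Stratified analysis does not cure the odd/even allocation, or the exclusion of mutation carriers from the study arm only, after allocation (Protocol, Patient Selection and Inclusion Criteria). Those are systematic routes to imbalance, not chance.

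**What to change.** - Make the primary analysis of clinical response and of mortality a Cochran-Mantel-Haenszel test **without continuity correction**, stratified by respiratory support before the first dose: invasive ventilation, oxygen, or room air. Check which form the SPSS output reports.
- Add that three-level variable explicitly to the baseline record, with its time relative to the first dose.
- Report the Mantel-Haenszel odds ratio or risk difference with a 95% confidence interval.
- Keep the unstratified chi-square as a sensitivity analysis. Do not add hospital to the primary strata: at 60 patients it can cancel the gain.
- Fix this before outcomes are seen, since adjustment chosen after an imbalance appears would look data-driven.

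The cost is a SAP amendment and one baseline field, plus up to about one point of power if entry support proves weakly prognostic.
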